9.1.14 Concurrent conditions

Concurrent conditions are defined as symptoms or diseases that are present at the time of the informed consent. Abnormal findings from physical examination at the start of the run-in period will be regarded as concurrent conditions at the discretion of the principal investigator or investigator.

9.1.15 Pregnancy

If pregnancy of a participant is found during the study, with agreement of the female participant, the principal investigator or investigator will inform her obstetrics/gynecology doctor about the fact of her participation in the clinical study at the onset of the pregnancy, as well as details of the study drug.

All pregnancies reported during the study will be followed up to their outcomes by the principal investigator or investigator, with agreement of the participants with pregnancy. The outcome of pregnancy, including any premature labor, will be reported to the sponsor, using a designated report form. Assessment after childbirth will also be performed.

9.1.16 Documentation of withdrawals before study treatment

For all participants withdrawn before the start of study treatment after signing the consent form, the case report form will be completed.

The following data will be recorded in the case report form:

- Date of informed consent
- Date of birth
- Sex
- Eligibility
- Reason for withdrawal

The main reason for the withdrawal before the start of study treatment will be recorded, using the following classification:

- Not fulfilling all of the inclusion criteria, or meeting any of the exclusion criteria
- Major protocol deviation
- Lost to follow-up
- Voluntary withdrawal (The reason should be specified)
- Discontinuation of the entire study
- Pregnancy
- Other (The reason should be specified)

Participant identification codes assigned to the participants withdrawn before the start of study treatment must not be reused.

9.2 Monitoring of Treatment Compliance in Participants

At each visit, the principal investigator or investigator will assess the participant's compliance with the study drug and antidepressant medication. The compliance status will be classified into 4 categories: nearly all of the prescribed doses were taken ($\geq 90\%$), most of the prescribed doses were taken ($\geq 70\%$), about half of the prescribed doses were taken ($\geq 50\%$), or less than half of the prescribed doses were taken ($< 50\%$).

Throughout the study period, participants will be reinstructed about medication. If poor compliance with the study drug after the previous visit, such as $< 50\%$ of prescribed doses, is found and does not improve, the participant may be withdrawn as appropriate.

9.3 Schedule of Examinations and Observations

The schedule for all examinations, observations, and evaluations is shown in Appendix A. The principal investigator or investigator will perform the following examinations, observations, and evaluations as scheduled.

9.3.1 Start of the run-in period (VISIT 1)

After informed consent, the following data will be obtained by physical examination and other examinations. In addition, participants will be instructed to keep a sleep diary and to perform actigraphy recording for 1 week before VISIT 2 (i.e., Week -1 to Week 0). Eligibility of participants will be confirmed against the inclusion and exclusion criteria given in Section 7.0. For documentation of participants withdrawn during the run-in period, the procedures in Section 9.1.13 should be followed.

During the run-in period, the following examinations, observations, and evaluations will be performed:

- Informed consent

- Demographic data, medical history, prior medication, history of insomnia, depressive episodes
- Physical examination
- Height, body weight and BMI
- Concurrent medications
- Concurrent conditions
- HAM-D17
- C-SSRS (baseline)

9.3.2 Start of the study treatment period (VISIT 2)

At the start of administration of the study drug, the following examinations, observations, and evaluations will be performed.

For participants fulfilling all of the inclusion criteria and not meeting any of the exclusion criteria given in Section 7.0, the principal investigator or investigator will instruct to start taking the study drug according to Section 6.1.

- Physical examination
- Body weight
- Concomitant medications
- Concurrent conditions
- HAM-D17
- Assessment of the actigraphy data from Week -1 to Week 0
- Sleep diary
- 3DSS
- C-SSRS (after last assessment)

9.3.3 Treatment period (VISIT 3)

During the treatment period (VISIT 3), the following examinations, observations, and evaluations will be performed.

- Physical examination
- Body weight
- Concomitant medications
- HAM-D17
- Assessment of actigraphy data from Week 3 to Week 4
- Sleep diary

- Adverse events
- 3DSS
- Treatment compliance
- C-SSRS (after last assessment)

9.3.4 At completion (VISIT 4) or withdrawal

Final visit will be made at 8 weeks after the start of study treatment, when the following examinations, observations, and evaluations will be performed. In withdrawn participants, the same examinations, observations, and evaluations will be performed at withdrawal from the study.

- Physical examination
- Body weight
- Concomitant medications
- HAM-D17
- Assessment of actigraphy data from Week 7 to Week 8*
- Sleep diary
- Adverse events
- 3DSS
- Treatment compliance
- C-SSRS(after last assessment)
- PGI

For all participants given the study drug, the study completion/withdrawal status will be recorded in the case report form.

10.0 Pretreatment Event and Adverse Event

10.1 Definitions

10.1.1 Adverse events

An adverse event is any untoward medical occurrence in a patient or clinical investigation participant administered a pharmaceutical product (including a study drug) and which does not necessarily have to have a clear causal relationship with this treatment.

An adverse event can therefore be any unfavorable or unintended sign (including an abnormal laboratory finding, for example), symptom, or disease temporally associated with the use of a medicinal product, whether or not considered related to the medicinal product.

10.1.2 Considerations for Adverse Events

Generally unfavorable findings are described below:

- Newly diagnosed disease or unexpected aggravation of existing symptom (intermittent event of an existing symptom is not considered an adverse event)
- Requiring action or medical practice
- Requiring invasive diagnostic treatment
- Requiring discontinuation or a change in the dose of the study drug
- Considered unfavorable by the investigator or the subinvestigator

Diagnosis name and signs/symptoms:

Adverse events shall be recorded by diagnosis name. Accompanying signs (including abnormal laboratory values, abnormal ECG findings) and symptoms shall not be recorded as adverse events. If an adverse event could not be expressed by a diagnosis name, the signs or symptoms shall be recorded as the adverse event.

Laboratory test values and ECG findings:

Abnormal laboratory values and ECG findings shall be recorded as adverse events when the principal investigator or investigator judges the results are clinically problematic (in other words, when certain action or medical practice is required, or when the principal investigator or the investigator judges the change has exceeded the normal physiological variation range of the research subject). Retest and/or continued monitoring of an abnormality are not considered medical practice. Also, repeated or additional

conduction of non-invasive tests for verification, evaluation, and monitoring of an abnormality are not considered medical practice.

However, when abnormal laboratory values and ECG findings are the accompanying symptoms of a disease diagnosed as an adverse event (e.g., increased creatinine due to renal dysfunction, etc.), the adverse event shall be handled by its diagnosis name.

Pre-existing conditions (at start of treatment period):

A disease or symptoms that had been present since before the start of observation period shall be regarded as a concurrent disease and not an adverse event. When a concurrent medical condition is aggravated, the aggravation shall be determined as an adverse event and the investigator or the subinvestigator shall record on the CRF that the adverse event is an aggravation of the concurrent disease (e.g., "aggravation of hypertension," etc.).

If a research subject has a pre-existing episodic condition (e.g., asthma, epilepsy), each episode shall be recorded as an adverse event if the episodes become more frequent, serious, or severe in nature. If a research subject has a chronic concurrent condition (e.g., cataracts, rheumatoid arthritis), worsening of the condition shall be recorded as adverse event if the degree of the worsening exceeds that which would be expected. The principal investigator or investigator shall ensure that the adverse event term to be recorded represents the change in the condition from baseline (e.g. "worsening of...").

Worsening of adverse events:

If a research subject experiences a worsening of the adverse event after a change to the study drug, or secondary signs and symptoms are caused by the adverse event, the worsening or the secondary signs and symptoms shall be recorded as a new adverse event on the CRF. The principal investigator or investigator shall use an adverse event term that explicitly means a change of the condition (e.g., "worsening of...").

Change of severity of adverse events:

If the research subject experiences changes in the severity of an adverse event, the event shall be recorded once, at its peak severity.

Previously planned surgery or treatment:

Preplanned surgeries or interventions that were scheduled before study treatment shall not be considered adverse events. However, when the existing symptom is aggravated to a degree requiring emergency surgery or treatment, the condition or the event shall be considered an adverse event. A concurrent disease that resulted from previously planned surgery shall be reported as an adverse event.

Non-urgent surgery or treatment:

Non-urgent surgery or treatment that does not induce a change in the condition of a research subject (cosmetic surgery, etc.) shall not be considered an adverse event; however, it shall be recorded in the source documents. Concurrent diseases due to a non-urgent surgery shall be reported as an adverse event.

The Insufficient clinical response (lack of efficacy)

Insufficient clinical response, efficacy, or pharmacological action shall not be recorded as an adverse event. The principal investigator or investigator shall make the distinction between worsening of a pre-existing condition and lack of therapeutic efficacy.

Overdose of the study drug

Overdose of any medication without manifested symptoms shall not be recorded as an adverse event, but the overdose shall be recorded on the "Overdose" page of the CRF. Any manifested symptoms shall also be recorded as adverse events on the "Adverse events" of the CRF.

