8.1.2 Overdose

Overdose is defined as intentional or accidental administration of the study drug at a higher dose than that specified in the protocol, either by a health professional or by the research subject.

To consistently collect important safety information about overdose, the principal investigator or investigator(s) shall record all cases of overdose on the "Overdose" page of the CRF, irrespective of the presence or absence of accompanying adverse event. Adverse events associated with overdose shall be recorded on the "Adverse events" page of the CRF, in accordance with the procedures described in Section 10.0, "ADVERSE EVENTS."

In addition, serious adverse events associated with overdose shall be recorded in accordance with the procedures described in Section 10.2.2, "Collection and reporting of SAEs."

In the event of overdose, the principal investigator or investigator shall treat the subject as required based on symptoms

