10.2.2 Collection and reporting of serious adverse events

When a serious adverse event develops during the period of collecting adverse events, it shall be reported according to the following procedures.

At the time of onset of a serious adverse event or notification of the onset by the research subject, the principal investigator shall report the serious adverse event to the chief executive of the study site immediately, and the sponsor or CRO to whom the sponsor has entrusted responsibility shall notify the principal investigator of the study site.

The principal investigator shall then report the serious adverse event to the sponsor (for the contact information, refer to the attachment) within 1 day of becoming aware of the event onset. Further, the investigator shall submit a formal report within 10 calendar days to the sponsor.

Furthermore, it shall be mandatory to include the contents below in the report to be submitted to the sponsor within 1 working day, and other items shall be reported as far as possible.

- Brief description of adverse event and the reason for why it was determined as serious

- Research subject ID number
- Name of investigator or the subinvestigator
- Name of the study drug
- Determined causal relationship

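### The rule that a symptom-free overdose is not an adverse event makes no exception for intentional overdose, and the protocol does not say how the suicidal act behind one is to be recorded or reported

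*Protocol*

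**What the plan says.** Protocol 8.1.2 sets the definition: "Overdose is defined as intentional or accidental administration of the study drug at a higher dose than that specified in the protocol". Every such case goes on the Overdose page, "irrespective of the presence or absence of accompanying adverse event". Adverse events that accompany an overdose go on the adverse event page, and "serious adverse events associated with overdose shall be recorded in accordance with the procedures described in Section 10.2.2".

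Protocol 10.1.2 has its own paragraph on overdose, headed as concerning the study drug. Its text is wider: "Overdose of any medication without manifested symptoms shall not be recorded as an adverse event". The same sentence then requires an entry on the dedicated Overdose page instead. Symptoms, if any, are recorded as adverse events. Intent is not mentioned.

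Expedited reporting is in Protocol 10.2.2 and begins from a serious adverse event: "When a serious adverse event develops during the period of collecting adverse events, it shall be reported according to the following procedures". Notification of the ethics committee and the other sites (Protocol 10.3.1) begins from a serious adverse event report. The safety tables in Protocol 13.1.6 and SAP 8.1 count treatment-emergent adverse events. SAP 9 includes overdose among the data to be listed.

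Both protocol versions in the file carry the same overdose wording, so this is not a difference between versions.

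**The concern.** Participants have a DSM-5 diagnosis of depression and take an antidepressant, and Protocol 5.1.2 makes safety the secondary objective. A deliberate overdose is one of the safety events that matter most in such a population, whether or not it produces symptoms. A rule that classifies by symptoms alone treats a suicide attempt without symptoms in the same way as a tablet taken twice by mistake.

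What is at stake is mainly prompt reporting: the one-day report to the sponsor and the onward notification. The summary tables come second. The other suicide-related data do not clearly fill the gap. C-SSRS results are deliberately kept out of the CRF (Protocol 9.1.12). HAM-D17 item 11 is recorded (9.1.9), and sign of suicide is a withdrawal reason (7.5 item 8), but neither is stated to start safety reporting.

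**Working it through.** No arithmetic applies; the documents contain no figure to reproduce. The check is to follow a case through the text.

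**Case A: intentional overdose of study drug, no symptoms.**
1. It is an overdose under 8.1.2, which includes intentional acts.
2. It must be entered on the Overdose page (8.1.2 and 10.1.2).
3. The overdose itself may not be recorded as an adverse event (10.1.2).
4. The overdose-specific link in 8.1.2 to section 10.2.2 covers only serious adverse events associated with the overdose. On a literal reading of step 3 there is none.
5. The trigger in 10.2.2 is not met, so that in 10.3.1 is not met either. No reporting deadline is attached to the Overdose page.
6. The tables in Protocol 13.1.6 and SAP 8.1.1 and 8.1.2 have no overdose category. The case appears only in the SAP 9 listing.

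**Is there another route for the suicidal act?** The bar in 10.1.2 is on the overdose. It does not mention the act or intent behind it. Three general provisions could apply:
- 10.1.2 lists findings that need medical action, that require the study drug to be discontinued, or that are "Considered unfavorable by the investigator or the subinvestigator".
- 10.1.3 item 3 covers hospitalization.
- 10.1.3 item 6 covers medically important events. Table 10.a names neither suicide attempt nor overdose, but nothing excludes them.

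So a route exists, but it is implicit. It asks the investigator to prefer a general criterion over a specific prohibition in the same section.

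**Case B: intentional overdose of the antidepressant, no symptoms.** The result depends on which scope a site applies.

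| Reading | Overdose page | Bar on adverse event record |
|---|---|---|
| 10.1.2 text governs (any medication) | Required | Applies |
| 8.1.2 and the 10.1.2 heading govern (study drug) | Not required | Does not apply; general criteria decide |

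The two readings give opposite answers in both columns.

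**Case C: either overdose with symptoms.** The symptoms are recorded as adverse events and the ordinary seriousness assessment follows. There is no gap for the symptoms themselves.

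**The case against.** The strongest reply is that the plan captures these events by design. Every study-drug overdose goes on a dedicated page, CRF data reach the sponsor, and the SAP lists them. Keeping symptom-free overdoses apart from adverse events is a stated choice and a reasonable one for accidental cases. A deliberate overdose judged a sign of suicide would also end participation (Protocol 7.5 item 8 with 7.6), which arguably meets the 10.1.2 criterion of requiring discontinuation. A worsening of depression could be recorded as aggravation of a concurrent condition. Exclusion 7 and the HAM-D17 ceiling of 16 make such events less likely.

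Much of this stands, and it rules out three stronger readings that a reader might infer:
- *A symptom-free self-poisoning can never enter the adverse event or serious adverse event system.* The text does not support this. The prohibition concerns the overdose, and the general criteria leave a route for the suicidal act.
- *An antidepressant overdose would appear in no overdose or adverse event record.* This would require a site to apply the first half of the 10.1.2 sentence to any medication and ignore the second half, which requires the Overdose page. Under either consistent reading in the table, at least one form of record is required or remains open.
- *The harm can be stated as one case in the 30 planned patients.* That is division on a hypothetical event, and it assumes the event would be classed as serious. No document gives a rate.

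The reply does not remove the remaining problem. An entry on the Overdose page is not a safety report, and the implicit route conflicts with a mandatory instruction. With about five sites and no guidance, the same event could be reported within a day at one site and appear only in a listing from another.

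**Conclusion.** The point holds as a gap in the recording and reporting rules. Protocol 10.1.2 excludes symptom-free overdoses from adverse event recording without regard to intent, although 8.1.2 expressly includes intentional overdose. Taken literally, that steers a deliberate symptom-free overdose away from expedited reporting and from the safety tables. Neither document says whether the act behind it is an adverse event or a serious one. The scope of the overdose rule is inconsistent between 8.1.2, the 10.1.2 heading and the 10.1.2 text.

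The efficacy analyses are not affected. The size in practice is unknown and probably small in number of events; the weight comes from the seriousness of the event and the population studied. The conclusion rests on the protocol and SAP as written. The CRF and the sponsor's safety procedures are not among the documents and might contain further instructions. The change is worth making because an explicit rule, and not merely missing detail, points sites in the wrong direction for reporting.

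**What to change.** 1. In Protocol 10.1.2, limit the exclusion to symptom-free overdoses without known or suspected self-harm intent.
2. In the same place, state that an overdose with such intent is recorded as an adverse event whether or not symptoms appear, is assessed for seriousness under 10.1.3, and is reported under 10.2.2 if serious.
3. Use one scope, study drug or any medication, for the Overdose page in 8.1.2 and in both the heading and text of 10.1.2.
4. If the Overdose page does not already record whether the overdose was intentional or accidental, add that field. This cannot be judged without the CRF.

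These changes concern recording and reporting only and leave the treatment of an overdose untouched. They need a few sentences in the protocol and possibly one CRF field. Intentional cases recorded as adverse events would then enter the existing SAP 8.1 tables without a new analysis. The downside is an occasional additional adverse event or serious adverse event report.

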10.1.3 Serious adverse events

Of all the unfavorable medical events that develop with administration of drugs (irrespective of dose), a serious adverse event is an event that:

1. results in death,
2. is life threatening^{*},
3. requires inpatient hospitalization or prolongation of existing hospitalization,
4. results in persistent or significant disability/incapacity,
5. leads to a congenital anomaly/birth defect, or
6. other medically significant condition: a medically important event that causes a risk to a research subject even if it is not immediately life-threatening and does not result in death or hospitalization, or requires an action or treatment to prevent the results described in 1 to 5 above. Points described in the Takeda Medically Significant Adverse Event List (Table 10 (a)) are included in this section.

* The term "life threatening" refers to an event in which the research subject was at risk of death at the time of the event; it does not refer to an event that hypothetically might have caused death if it were more severe.

Table 10.a Takeda Medically Significant AE List

| | |
|--|---|
| Acute respiratory failure/acute respiratory distress syndrome (ARDS) | Hepatic necrosis Acute hepatic failure |
| Torsades de pointes/ ventricular fibrillation/ventricular tachycardia | Anaphylactic shock Acute renal failure |
| Malignant hypertension | Pulmonary hypertension |
| Convulsive seizure (including convulsion and epilepsy) | Pulmonary fibrosis (including interstitial pneumonia) |
| Agranulocytosis | Neuroleptic malignant syndrome/ malignant hyperpyrexia |
| Aplastic anemia | Spontaneous abortion/ stillbirth and fetal death |
| Toxic epidermal necrolysis/ Oculomucocutaneous syndrome (Stevens-Johnson syndrome) | Confirmed or suspected transmission of infection by a medicinal product Confirmed or suspected endotoxin shock |

10.1.4 Severity of adverse events

The severity of adverse events shall be classified and defined as shown below.

| | |
|----------|---|
| Mild | The event is transient and easily tolerated by the subject. |
| Moderate | The event interrupts the subject's usual activities. |
| Severe | The event causes considerable interference with the subject's usual activities. |

